9.4 Statistical Analyses

The statistical analysis plan will be developed and finalized before database lock. Below is a summary of the timing and methods for the planned statistical analyses. To preserve study integrity, the final analysis will be conducted and reported following the end of study, as defined in Section 4.4.1.

9.4.1 Planned Analyses

9.4.1.1 Interim Analysis

Safety data will be reviewed on an ongoing basis. A data review team (DRT), internal to Amgen but external to the study team, will assess after every fifth non-replaceable subject has been dosed and given an opportunity to complete MDMP. Refer to Section 4.2.1 for details on replacement of subjects. Based on their reviews, the DRT will make recommendations to Amgen regarding the continuation of the study. There will be no formal guidelines to stop for safety. The DRT will consist of 3 or more members including 2 or more clinicians with relevant specialties and 1 or more statisticians. The DRT will be supported by an independent statistician who is responsible for preparing reports that describe the ongoing clinical study data. Details regarding the responsibilities of the DRT and the independent statistician will be described in the DRT Charter.

9.4.1.2 Primary Analysis

The primary analysis will occur when all subjects complete the end of study Visit 30 days (+ 3 days) after the last dose of up to 4 cycles of blinatumomab or withdraw from the study.

Date: 21 April 2022 Page 67 of 108

9.4.1.3 Final Analysis

The primary analysis will also be the final analysis.

9.4.2 Methods of Analyses

9.4.2.1 General Considerations

Descriptive statistics for demographic and safety will be summarized as appropriate. For categorical variables, the number and percentage of subjects in each category will be summarized. Continuous variables will be summarized by n, mean, standard deviation, median, Q1 (25th percentile), Q3 (75th percentile), minimum, and maximum values.

9.4.2.2 Efficacy Analyses

Endpoint	Statistical Analysis Methods
Primary	Not applicable
Secondary	Not applicable
Exploratory	Not applicable.

9.4.2.3 Safety Analyses

9.4.2.3.1 Analyses of Primary Safety Endpoint(s)

Endpoint	Statistical Analysis Methods
Primary	Subject incidence rate of primary endpoint (grade 3 or 4 CRS, NT or any adverse event resulting in hospitalization during MDMP) will be summarized and accompanied by 2-sided 95% exact binomial confidence intervals (Clopper and Pearson, 1934).
Key Secondary	Time from first onset of the key secondary endpoint event to therapeutic intervention will be summarized as continuous variable with count of non-missing, mean, median, standard deviation, minimum and maximum for those experiencing the endpoint. Type of therapeutic intervention will be tabulated with n (see Section 9.4.2.4). If there are events that prevent the occurrence of therapeutic intervention, censoring based approach such as Kaplan-Meier may be used.
Secondary	The statistical analysis methods for adverse event and other safety endpoints are described in Section 9.4.2.3.2 through Section 9.4.2.3.4.
Exploratory	Not applicable

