The above benefit risk assessment supports the conduct of this clinical trial. Reference should be made to the Investigator's Brochure for further data on blinatumomab.

Date: 21 April 2022 Page 34 of 108

Training material will be provided by CH with further information on the digital devices used in the study.

3. Objectives and Endpoints

Objectives		Endpoints
Primary		
To determine the safety of blinatumomab administrat MDMP (defined as the first cycle 1 and first 2 days of outpatient blinatumomab in	ion, during the st 3 days of cycle 2 of	 Incidence of grade 3 and/or 4 CRS, NT or any adverse event (AE) requiring hospitalization (SAE) during MDMP.
Secondary		
To determine the time from of grade 3 or 4 vital sign, or clinical change to theraped (any measurable action tall performed on the subject of the clinical parameters deduring the MDMP.	or significant utic intervention ken by or due to onset of	Time (in minutes) from first onset of fever, hypotension, hypoxia, other grade 3 or 4 vital sign including seizure or neurological change (grade 3-limiting self-care activities of daily living [ADL]) to therapeutic intervention ^a
Evaluate the safety and to blinatumomab administers as an outpatient		 Overall incidence and severity of treatment-emergent adverse events (TEAE) and adverse events of interest in particular CRS and NT.
Evaluate the impact of coroutpatient blinatumomab to patient reported outcome health status (GHS), and (QoL).	reatment on (PRO), global	 European Organisation for Research and Treatment of Cancer (EORTC) validated electronic version of QLQ-C30.
Estimate healthcare resou associated with treatment		 TEAEs that resulted in hospitalizations TEAEs that resulted in surgeries. TEAEs that resulted in the use of concomitant medications TEAEs that resulted in the use of device/procedure intervention.

ADL = activities of daily living; AE = adverse event; CG = caregiver; CRS = cytokine release syndrome; EMS = Emergency Medical Service; EORTC = European Organisation for Research and Treatment of Cancer; GHS = global health status; HCP = Health Care Provider; IV = intravenous; MDMP = mandatory device monitoring period; NT = neurotoxicity; PO = by mouth; PRO = patient reported outcomes; QLQ-30 = Quality of Life of Cancer Patients; QoL = quality of life; SAE = serious adverse event; TEAE = treatment-emergent adverse event.

Date: 21 April 2022 Page 35 of 108

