8.2.5.1.2 Serious Adverse Events

The investigator is responsible for ensuring that all **serious adverse events** observed by the investigator or reported by the subject that occur from signing of the informed consent through the end of study visit are reported using the Event**s** CRF.

All **serious adverse events** will be collected, recorded and reported to the sponsor or designee within 24 hours of the investigator's **awareness** of the event, as indicated in Section 11.4. The investigator will submit any updated **serious adverse event** data to the sponsor within 24 hours of it being available.

Since the criteria for grade 4 in the CTCAE grading scale differs from the regulatory criteria for serious adverse events, if adverse events correspond to grade 4 CTCAE toxicity grading scale criteria (eg, laboratory abnormality reported as grade 4 without manifestation of life-threatening status), it will be left to the investigator's judgment to also report these grade 4 abnormalities as serious adverse events. For any adverse event that applies to this situation, comprehensive documentation of the event's severity must be recorded in the subject medical records.

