- For situations when an adverse event or serious adverse event is due to primary tumor type being studied report all known signs and symptoms. Death due to disease progression in the absence of signs and symptoms should be reported as the primary tumor type (eg, metastatic pancreatic cancer). Note: The term "disease progression" should not be used to describe the adverse event.
- The signs, symptoms, and/or clinical sequelae resulting from lack of efficacy will be reported as adverse event or serious adverse event if they fulfill the definition of an adverse event or serious adverse event. Also, "lack of efficacy" or "failure of expected pharmacological action" also constitutes an adverse event or serious adverse event.

Date: 21 April 2022 Page 85 of 108

Events NOT Meeting the Adverse Event Definition

• Medical or surgical procedure (eg, endoscopy, appendectomy): the condition that leads to the procedure is the **adverse event**.

- Situations in which an untoward medical occurrence did not occur (social and/or convenience admission to a hospital).
- Anticipated day-to-day fluctuations of pre-existing disease(s) or condition(s) present or detected at the start of the study that do not worsen.

Definition of Serious Adverse Event

A Serious Adverse Event is defined as any untoward medical occurrence that, meets at least 1 of the following serious criteria:

Results in death (fatal)

Immediately life-threatening

The term "life-threatening" in the definition of "serious" refers to an event in which the subject was at risk of death at the time of the event. It does not refer to an event, which hypothetically might have caused death, if it were more severe.

Requires inpatient hospitalization or prolongation of existing hospitalization

In general, hospitalization signifies that the subject has been detained (usually involving at least an overnight stay) at the hospital or emergency ward for observation and/or treatment that would not have been appropriate in the physician's office or outpatient setting. Complications that occur during hospitalization are an **adverse event**. If a complication prolongs hospitalization or fulfills any other serious criteria, the event is serious. When in doubt as to whether "hospitalization" occurred or was necessary, the **adverse event** is to be considered serious. Hospitalization for elective treatment of a pre-existing condition that did not worsen from baseline is not considered an **adverse event**.

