Results in persistent or significant disability/incapacity

The term disability means a substantial disruption of a person's ability to conduct normal life functions. This definition is not intended to include experiences of relatively minor medical significance such as uncomplicated headache, nausea, vomiting, diarrhea, influenza, and accidental trauma (eg, sprained ankle) which may interfere with or prevent everyday life functions but do not constitute a substantial disruption.

Is a congenital anomaly/birth defect

Date: 21 April 2022 Page 86 of 108

Other medically important serious event

Medical or scientific judgment is to be exercised in deciding whether **serious adverse event** reporting is appropriate in other situations such as important medical events that may not be immediately life-threatening or result in death or hospitalization but may jeopardize the subject or may require medical or surgical intervention to prevent 1 of the other outcomes listed in the above definition. These events are typically to be considered serious.

Examples of such events include invasive or malignant cancers, intensive treatment in an emergency room or at home for allergic bronchospasm, blood dyscrasias or convulsions that do not result in hospitalization, or development of drug dependency or drug abuse.

Definition of Adverse Device Effect

The detection and documentation procedures for adverse device effects described in this protocol apply to all medical devices provided for use in the study (see Section 6.1.2 for the list of medical devices).

Adverse Device Effect Definition

An adverse device effect is any **adverse event** related to the use of a combination product or medical device. Adverse device effects include, **but are not limited to**, **adverse events** resulting from insufficient or inadequate instructions for use, **adverse events** resulting from any malfunction of the device, or **adverse events** resulting from use error or from intentional misuse of the device.

A combination product is a product composed of any combination of a drug, a device, and a biological product. Each drug, device, and biological product included in a combination product is referred to as a "constituent part" of the combination product.

Recording Adverse Events and Serious Adverse Events

Adverse Event and Serious Adverse Event Recording

When an adverse event or serious adverse event occurs, it is the responsibility

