of the investigator to review all documentation (eg, hospital progress notes,
laboratory, and diagnostics reports) related to the event.

Date: 21 April 2022 Page 87 of 108

- The investigator will then record all relevant adverse event/serious adverse event information in the Event case report form (CRF).
- The investigator must assign the following mandatory adverse event attributes:
 - Adverse event diagnosis or syndrome(s), if known (if not known, signs or symptoms);
 - Dates of onset and resolution (if resolved);
 - Did the event start prior to first dose of investigational product;
 - Assessment of seriousness;
 - Severity (or toxicity defined below);
 - Assessment of relatedness to IP [blinatumomab], or other protocol-required therapies or devices [Current Wearable Health Monitoring System (CWHMS)];
 - Action taken; and
 - Outcome of event.
- If the severity of an **adverse event** changes from the date of onset to the date of resolution, record a single event for each level of severity on the Event**s** CRF.
- It is not acceptable for the investigator to send photocopies of the subject's medical records to sponsor/responsible contact research organization in lieu of completion of the Events CRF page.
- If specifically requested, the investigator may need to provide additional follow-up
 information, such as discharge summaries, medical records, or extracts from the
 medical records. In this case, all subject identifiers, with the exception of the
 subject number, will be blinded on the copies of the medical records before
 submission to Amgen.
- The investigator will attempt to establish a diagnosis of the event based on signs, symptoms, and/or other clinical information. In such cases, the diagnosis (not the individual signs/symptoms) will be documented as the adverse event/serious adverse event.

Evaluating Adverse Events and Serious Adverse Events

Assessment of Severity

The investigator will make an assessment of severity for each **adverse event** and **serious adverse event** reported during the study. The assessment of severity will be based on:

The Common Terminology Criteria for Adverse Events, version 5.0 which is available at the following location:

http://ctep.cancer.gov/protocolDevelopment/electronic applications/ctc.htm.

Protocol Number: 20190014

Product: Blinatumomab
Protocol Number: 20190014

Date: 21 April 2022 Page 88 of 108

Assessment of Causality

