2.1 Objectives and Endpoints

Objectives	Endpoints	
Primary		
• To determine the safety of outpatient blinatumomab administration, during the MDMP (defined as the first 3 days of cycle 1 and first 2 days of cycle 2 of outpatient blinatumomab infusion)	 Grade 3 and/or 4 CRS, NT or any adverse event (AE) requiring hospitalization (SAE) during MDMP. 	
Secondary		
• To determine the time from first detection of grade 3 or 4 vital sign, or significant clinical change to therapeutic intervention (any measurable action taken by or performed on the subject due to onset of the clinical parameters described above) during the MDMP	• Time (in minutes) from first onset of fever, hypotension, hypoxia, other grade 3 or 4 vital sign including seizure or neurological change (grade 3-limiting self-care activities of daily living [ADL]) to therapeutic intervention.	
 Evaluate the safety and tolerability of blinatumomab administered exclusively as an outpatient 	 Treatment-emergent adverse events (TEAE) and adverse events of interest in particular CRS and NT. 	
• Evaluate the impact of complete outpatient blinatumomab treatment on patient-reported outcome (PRO), global health status (GHS), and quality of life (QoL).	 European Organisation for Research and Treatment of Cancer (EORTC) validated electronic version of QLQ-C30. 	
Estimate healthcare resource utilization associated with treatment-related AEs	 Treatment-related TEAEs that resulted in hospitalizations. Treatment-related TEAEs that resulted in surgeries. Treatment-related TEAEs that resulted in the use of concomitant medications. Treatment-related TEAEs that resulted in the use of device/procedure intervention. 	

ADL = activities of daily living; AE = adverse event; CG = caregiver; CRS = cytokine release syndrome; EMS = Emergency Medical Service; EORTC = European Organisation for Research and Treatment of Cancer; GHS = global health status; HCP = Health Care Provider; IV = intravenous; MDMP = mandatory device monitoring period; NT = neurotoxicity; PO = by mouth; PRO = patient-reported outcomes; QLQ-30 = Quality of Life of Cancer Patients; QoL = quality of life; SAE = serious adverse event; TEAE = treatment-emergent adverse event.

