9.5.2 Analyses of Secondary Efficacy Endpoint(s)

Not Applicable.

9.5.3 Analyses of Exploratory Efficacy Endpoint(s) Not Applicable.

- 9.6 Safety Analyses
- 9.6.1 Analyses of Primary and Key Secondary Safety Endpoint(s)

Endpoint	Statistical Analysis Methods				
Primary	Subject incidence rate of primary endpoint (grade 3 or 4 CRS, NT or				
	any adverse event resulting in hospitalization during MDMP) will be				
	summarized and accompanied by 2-sided 95% exact binomial				
	confidence intervals (Clopper and Pearson, 1934). This endpoint will				
	be analyzed using PAS and repeated using interim analysis set.				
Кеу	TTI as defined in section 5 of SAP will be summarized as continuous variable with number of non-missing and valid TTI with mean, median, standard deviation, minimum and maximum.				
Secondary					
	Number and percent of subjects who had received at least one				
	therapeutic intervention (as defined in section 5 of SAP) will be				
	summarized in total and by types of intervention. Total number of				
	therapeutic interventions and type of therapeutic intervention will be				
	tabulated.				
	Number and percent of subjects with at least one alarm triggered will				
	be summarized in total and by reasons of alarm trigger. Total number				
	of alarms triggered and reasons for each alarm trigger (as specified				
	below) will be tabulated.				
	Technical				
	Patient message				
	Physiological – Axillary temperature				
	Physiological – Systolic blood pressure				
	Physiological – Spo2				
	Physiological – Respiratory rate				
	Physiological – Pulse rate				
	Descriptive statistics for number of alarms triggered and therapeutic				
	interventions received per person will also be presented.				
	This endpoint will be analyzed using PAS and repeated using interim analysis set.				

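### The primary safety endpoint never names death, its analysis rows say hospitalization must result while its definitions say it must be required, and the SAP drops the MDMP adverse event tables the protocol plans

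*Protocol*

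**What the plan says.** **Analysis wording.** Protocol Section 9.4.2.3.1: "Subject incidence rate of primary endpoint (grade 3 or 4 CRS, NT or any adverse event resulting in hospitalization during MDMP) will be summarized". The primary row of SAP Section 9.6.1 begins "Subject incidence rate of primary endpoint (grade 3 or 4 CRS, NT or" and continues in the same terms, on the Primary Analysis Set (PAS).

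**Definition wording.** The protocol synopsis and Section 3 give "Incidence of grade 3 and/or 4 CRS, NT or any adverse event (AE) requiring hospitalization (SAE) during MDMP". SAP Section 2.1 has "any adverse event (AE) requiring hospitalization (SAE) during MDMP". Protocol Section 2.1 also says *requiring*, without the bracketed SAE tag. Protocol Section 4.1 and SAP Section 3.1 point to protocol Section 3 and SAP Section 2.1 as the places where endpoints are defined.

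**Seriousness.** Protocol Section 11.4 lists death ("Results in death (fatal") and inpatient hospitalization as separate serious criteria.

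**Adverse event tables.** Protocol Section 9.4.2.3.2 plans tables, including fatal events, on the Safety Analysis Set (SAS) and repeats the treatment-emergent analysis for the MDMP on the PAS. SAP Section 9.6.2 includes a fatal table but assigns all its tables to the SAS and mentions no MDMP repeat. SAP Section 9.6.8 keeps the MDMP repeat for exposure. SAP Section 10, the list of changes from the protocol, does not mention the dropped tables.

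**The concern.** The primary result is a safety statement about giving the first days of each cycle at home instead of in hospital. A reader will assume that a death in that window counts as an event. As the analysis rows stand, a programmer following them would count it only if the subject had been hospitalized or had a grade 3 or 4 CRS or NT record. One following the definitions could argue that a fatal event at home required hospitalization and count it. Two careful analysts could therefore report different primary counts from the same data.

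The missing tables make this worse. If the endpoint does not capture such a death, an adverse event table restricted to the MDMP is where a reader would look next, and the SAP does not plan one.

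**Working it through.** **1. The plan's own figure.** Inputs from protocol Section 9.2 and SAP Section 3.2: N = 45, event probability 38%, about 17 events, expected upper limit 53.5%. The interval method in protocol Section 9.4.2.3.1 is two-sided 95% exact binomial.

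- Expected events: 45 × 0.38 = 17.1.
- Exact upper limit for x events: the 0.975 quantile of Beta(x + 1, N − x). For x = 17, Beta(18, 28) gives 53.46%.
- Averaged over Binomial(45, 0.38), the upper limit is 53.52%.

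Both round to 53.5%, so the plan's arithmetic is right. The point concerns definition.

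**2. Which subject falls through.** Take a death during the MDMP and apply the analysis row.

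- *CRS or NT.* The CRS scale printed in protocol Section 11.8 stops at grade 4, and NT is defined there as grade 3 or above. When severity changes, Section 11.4 tells the investigator to "record a single event for each level of severity". A fatal CRS or NT would therefore usually carry a grade 3 or 4 record and be counted.
- *Hospitalized.* Section 11.4 lets detention in an emergency ward count as hospitalization, so a subject who reaches one is normally counted.
- *What remains.* A fatal event outside CRS and NT, with neither admission nor an emergency-ward stay. Neither limb is met.

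**3. The timing rule.** SAP Section 5 places an event in the MDMP by its onset: within 72 hours of the first dose in cycle 1 or 48 hours in cycle 2. A cycle lasts 6 weeks (42 days) and the first window covers 3 days, so about 42 − 3 = 39 days separate the windows. An event that starts in that gap and kills the subject in the cycle 2 window is not an MDMP event by onset. Adding only fatal events with onset in the window would still miss that death.

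**4. Size of one reclassified subject.** The step is 1/45 = 2.2 points. The lower limit is the 0.025 quantile of Beta(x, N − x + 1).

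| Events without the death | Rate (95% CI) | With it counted | Rate (95% CI) |
|---|---|---|---|
| 17 (the plan's expectation) | 37.8% (23.8–53.5) | 18 | 40.0% (25.7–55.7) |
| 10 (assumed) | 22.2% (11.2–37.1) | 11 | 24.4% (12.9–39.5) |
| 5 (assumed) | 11.1% (3.7–24.1) | 6 | 13.3% (5.1–26.8) |

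The documents give no rate of MDMP deaths, so the expected number of such subjects cannot be calculated.

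**5. The tables.** Setting protocol Section 9.4.2.3.2 beside SAP Section 9.6.2, the MDMP repeat on the PAS has gone. SAP Section 5 still defines an adverse event during the MDMP, but no table in Section 9.6.2 uses the definition. The time-to-onset summaries there cover only infection, neurologic events and CRS.

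**The case against.** The strongest reply is that the analysis row is a shorthand and the definition lies elsewhere. The definitions say *requiring*, which can be read to take in a fatal event at home. That is a fair reading, and it is why an uncounted death is a consequence of the literal analysis wording and not a certainty. It does not remove the problem: the two wordings differ, both documents use the narrower one where the count is specified, and neither mentions death.

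The second reply is that the case is remote. A caregiver is present around the clock, emergency escalation is laid down, and an advanced facility is within an hour. This stands. The number affected may be zero, and one subject moves the estimate by 2.2 points against an interval about 30 points wide (53.5 − 23.8 = 29.7).

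Third, such a death would not be hidden, as a reader might infer. It would be reported as a serious adverse event and appear in the whole-study fatal table. SAP Section 9.2 also summarizes completion of the MDMP and reasons for leaving the study, and protocol Section 7.2.1 lists death as one. This stands too, but none of these outputs isolates fatal events in the window.

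A reader might also infer that the SAE tag widens the endpoint to every serious event. That would matter, because Section 11.4 gives serious events with no admission, such as "intensive treatment in an emergency room or at home for allergic bronchospasm". The documents point the other way: protocol Sections 1.1, 2.1 and 4.1 and SAP Section 3.1 refer to other SAEs that require hospitalization, which makes the tag a label for hospitalization.

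**Conclusion.** Two things hold. First, the analysis rows and the definitions differ on hospitalization, and none of them names death. On the literal analysis wording, an MDMP death outside CRS and NT with no admission or emergency-ward stay is scored event-free. The effect is 2.2 points per subject at N = 45, assuming the death is not already among the counted events. Second, and more plainly, the MDMP adverse event tables in the protocol are absent from the SAP and the omission is not listed.

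Both affect the primary estimate and its reporting. Safety surveillance is not shown to be deficient, and no hypothesis test or formal stopping guideline rests on the estimate.

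A reader might go further and call the 38% planning rate an error, since it is a rate of serious adverse events and not of the endpoint. The two sets do differ in both directions: some serious events involve no admission, and Section 8.2.5.1.2 notes that "the criteria for grade 4 in the CTCAE grading scale differs from the regulatory criteria for" serious events, so a grade 4 event need not be serious. But the documents do not show which set is larger, and the sample size rests on feasibility. The 38% is at most a planning proxy that could be labelled as one.

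**What to change.** 1. Add to the primary endpoint: death from any cause during the MDMP, or any adverse event with onset during the MDMP that is fatal. The first part covers a cycle 2 death from an event that began between the windows. The second covers an event that starts in the window and proves fatal later.
2. Choose between *requiring* and *resulting in* for hospitalization and say what it means. Remove the SAE tag, or state that it only labels hospitalization.
3. Use that one wording in all six places: the protocol synopsis, protocol Sections 2.1, 3 and 9.4.2.3.1, and SAP Sections 2.1 and 9.6.1. Changing only some of them would create new contradictions.
4. Restore the MDMP adverse event tables on the PAS in SAP Section 9.6.2, including serious and fatal events.
5. Optionally, describe the 38% as an SAE rate used as a planning proxy.

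The cost is one sentence repeated in six places and one restored set of tables. No new data are needed. Onset date, seriousness and outcome are mandatory adverse event attributes (protocol Section 11.4), and date of death is collected (Section 8.2.4.3). Where a death has no clock time, the date-based fallback that SAP Section 5 already applies to missing start times can be used.
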